Important medical events are those that may not be immediately life threatening, but are clearly of major clinical significance. They may jeopardize the subject, and may require intervention to prevent one of the other serious outcomes noted above. For example, drug overdose or abuse, a seizure that did not result in in-patient hospitalization, or intensive treatment of bronchospasm in an emergency department would typically be considered serious.

All adverse events that do not meet any of the criteria for serious should be regarded as non-serious adverse events.

c) Unanticipated Adverse Device Effect (UADE): A UADE is any serious adverse effect on health or safety, or any life-threatening problem or death caused by, or associated with, a device, if that effect, problem, or death was not previously identified in nature, severity, or degree of incidence in the investigational plan or application, or any other unanticipated serious problem associated with a device that relates to the rights, safety, or welfare of

subjects.

2. Recording of Adverse Events

All adverse events occurring during the study period will be recorded. The clinical course of each event will be followed until resolution, stabilization, or until it has been determined that the study intervention or participation is not the cause. Serious adverse events that are still ongoing at the end of the study period will be followed up to determine the final outcome. Any serious adverse event that occurs after the study period and is considered to be possibly related to the study intervention or study participation will be recorded and reported.

3. Relationship of AE to Study

The PI will determine the relationship of each adverse event to the study procedures. Relationship will be classified as definitely related, probably related, possibly related, or not related.

4. Reporting of Adverse Events and Unanticipated Problems

The Investigator will promptly notify the Penn IRB of all on-site unanticipated, Adverse Events that are related to the research activity. Other unanticipated problems related to the research involving risk to subjects or others will also be reported promptly. Written reports will be filed using the HS-ERA and in accordance with the Penn IRB timeline of 10 working days.

5. Follow-up Report

If an AE has not resolved at the time of the initial report and new information arises that changes the investigator's assessment of the event, a follow-up report including all relevant new or reassessed information (e.g., concomitant medication, medical history) should be submitted to the IRB. The investigator is responsible for ensuring that all SAEs are followed until either resolved or stable.

12. Management of Multi-Site Research

1. Study Sites:

- University of Pennsylvania
- Thomas Jefferson University

2. Management of Information

The management of multi-site information will be carried out entirely by the research team at the University of Pennsylvania. The research team at Thomas Jefferson University (TJU) will simply provide a list of patients implanted with the Inspire® hypoglossal nerve stimulator and their contact information. All reporting of unanticipated problems, reporting of interim results, and submission of protocol modifications will be executed by the research team at the University of Pennsylvania.

3. Management of Study Teams

The management of study teams will be carried out entirely by the research team at the

University of Pennsylvania. The research team at Thomas Jefferson University will simply provide a list of patients implanted with the Inspire® hypoglossal nerve stimulator and their contact information. All subsequent research-related activities (i.e., consent, enrollment, study procedures, compensation, etc.) will be carried out by the research team at the University of Pennsylvania. For this reason, the research team at the University of Pennsylvania will ensure the research team at Thomas Jefferson University has the most up-to-date version of the study protocol, consent documents, and other supporting materials; however, no study related activities will occur at Thomas Jefferson University.

The only information that will be communicated between the research team at Thomas Jefferson University to the research team at the University of Pennsylvania is a list of patients implanted at Thomas Jefferson University with an Inspire® hypoglossal nerve stimulator and their contact information. This list of PHI will be sent to the research team at the University of Pennsylvania with a HIPAA waiver.

The TJU study team roster and their credentials (e.g., CVs, CITI certificates, medical licenses) will be collected by the Penn research team and kept on file at Penn. TJU will notify Penn of any relevant personnel or credential changes.

Local consent requirements are not expected to vary between study sites, as both sites are located in the same city. However, the research team at TJU will notify the Penn research team of any relevant changes to institutional policy or site-specific circumstances in a timely manner. Penn's research team will then notify IRB of any resulting changes warranting IRB review.

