Full Study Title

Hypoglossal Nerve Stimulation for Obstructive Sleep Apnea on Sympathetic and Vascular Function

Short Study Title CARDIOSA-12

Principal Investigator
[name], MSCR
Department of Otorhinolaryngology

Co-Investigator
[name]
Department of Otorhinolaryngology

Sponsors

American Heart Association
American Sleep Medicine Foundation

Protocol Version Number & Date Version 3.4 | 09/30/2021

- 1. Eligibility Criteria: All patients recruited into the study will have already been implanted with the Inspire® device. Additional inclusion criteria include:
 - As tolerating the therapeutic level during sleep can take time (weeks to months), all
 patients must be able to use the device at the therapeutic setting (> 20 hours per week for
 > 1 month) prior to enrollment based on compliance data.
 - The patients will be English-speaking and able to give written informed consent.

2. Exclusion Criteria

- Inspire® remote model 2500 or later is required. Patients with older remotes are not candidates due to limited adherence monitoring capabilities.
- Patients who have fallen asleep while driving resulting in accident or "near miss" accident within 1 year prior to HGNS implantation.
- Pregnant women will be excluded*
- Actively using positive airway pressure (PAP) therapy for treatment of OSA.
- Patients in whom the difference between sham and therapeutic voltages is within 0.1 V of 30% therapeutic voltage.
- * Women of child bearing potential must NOT be pregnant or plan on becoming pregnant. This study involves temporarily stopping treatment of obstructive sleep apnea, which may harm the fetus. If applicable, the patient will need to take a urine pregnancy test after enrollment (prior to washout #1), and again prior to washout #2.

3. Study Objectives

Primary Outcome Measure:

Change in mean 24-HOUR systolic ambulatory blood pressure values

Aim 1: Determine the impact of hypoglossal nerve stimulation on 24-hour systolic ambulatory blood pressure in this cohort of patients with moderate-severe obstructive sleep apnea

Hypothesis: The mean 24-hour systolic blood pressures will be improved at therapeutic levels of hypoglossal nerve stimulation and returned to pre-operative levels after 30-day sham period

Secondary Outcome Measures:

Change in mean 24-HOUR diastolic ambulatory blood pressure values

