Hypothesis: The pulse wave velocity parameters will be improved at therapeutic levels of hypoglossal nerve stimulation and returned to pre-operative levels after 30-day sham period

Change in Digit Symbol Substitution Test (DSST) score

Aim 5: Determine the impact of hypoglossal nerve stimulation on digital symbol substitution test score in this cohort of patients with moderate-severe obstructive sleep apnea

Hypothesis: The digital symbol substitution test score will be improved at therapeutic levels of hypoglossal nerve stimulation compared to after 30-day sham period

Change in Psychomotor Vigilance Test (PVT) score

[figure not shown]
Aim 6: Determine the impact of hypoglossal nerve stimulation on psychomotor vigilance test score in this cohort of patients with moderate-severe obstructive sleep apnea

Hypothesis: The psychomotor vigilance test score will be improved at therapeutic levels of hypoglossal nerve stimulation compared to after 30-day sham period

4. Procedures and Data Collection

4A. *Pre-Study Procedures:* All patients in the cohort will have undergone implantation of HGNS for OSA at the University of Pennsylvania or Thomas Jefferson University as part of their ongoing care for their OSA. HGNS therapy is not experimental and is not under investigation per se for efficacy in this study. **Figure 3** shows the study flow. Patients will receive compensation for travel and time spent in the study (\$100 per visit, plus \$10 parking reimbursement for each cardiovascular measurement visit; total=up to \$520). Reimbursement for parking may also be available. Compensation will be pro-rated, and will be in the form of mailed checks and/or ClinCards.

Figure 3: Study Flow

Note: We will leave +/- 14 days at each step to accommodate for scheduling issues, etc.

- 1. HGNS Device Implantation: Under general anesthesia, the HGNS device is implanted via 3 incisions: right neck (stimulation lead), right upper chest (pulse generator) and right lower chest (respiratory sensor). The incisions are connected via a tunneling device, integrating the system components. The pulse generator, using technology from cardiac pacemakers, utilizes the signal from the pressure sensor for timing of stimulation to the tongue nerve. Patients are monitored in post-anesthesia recovery until stable for discharge. The device remains "off" for 1 month to allow for adequate healing.

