- 2. HGNS Device Activation (1-month post-op): As part of usual care, patients return to the Otorhinolaryngology clinic 1 month post-operatively to undergo activation of the implanted device. At this visit, a functional threshold (in volts) is obtained based on tongue motion during device stimulation. The patient is provided detailed instructions on self-adjustment of stimulation levels using the remote control. For the next month, the patient will have steadily increased stimulation strength by 0.1V every 2-3 nights within the preset range until the upper limit is reached. The patient has the full support of the clinic nurse during this month to troubleshoot any issues.
- 3. Polysomnography (PSG) Titration (2-months post-op): Also as a component of usual care, two months after surgery, a level-I PSG (in accordance with 2014 American Academy of Sleep Medicine Manual for the Scoring of Sleep and Associated Events) is performed at the Sleep Center with standard parameters. Once asleep, the patient undergoes device titration of the HGNS starting at 0.2V below functional threshold. The voltage is sequentially increased by 0.1V until control of sleep-disordered breathing is achieved, providing "therapeutic amplitude" (treatment).

4B. Recruitment into the Cardiovascular Outcomes Study (variable months post-op): There are two different methods for recruitment:

1. An IRB-approved recruitment letter will be mailed to eligible HGNS patients, which will have contact information for the study team. If interested, the patient will reach out to the PI or the research study coordinator (RSC) who will mail or email (patient preference) a copy of the ICF for review. If contacted by the patient, RSC will obtain verbal consent and will coordinate an in-person visit with the patient at the Penn

- Otorhinolaryngology clinic. This visit will include informed consent and visit day one procedures. See 4C below.
- 2. At the patient's follow-up appointment, [name] will mention the study to the patient and provide a copy of the consent form. Informed consent discussion will be performed at this time. If the patient consents, study day 1 procedures will take place. See 4C below.
- Table 1: Age, gender, race, BMI, smoking status, Pre-op AHI, pre-op ODI, post-op AHI, post-op ODI, Months since implant, Hours of usage since activation, average weekly therapy use since last visit, diabetes status, HTN status, anti-HTN medications.

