- Eligibility Source documents: Initial consult note, pre-implant sleep study, pre-implant DISE report, HGNS titration report, HGNS efficacy sleep study report (if applicable), current medications list (reconciled), all Inspire® therapy reports leading up to enrollment.

4C. Study Timeline - Pages 5 to 10

- Enrollment (Study Day 1): HGNS therapy will be deactivated (set to 0.0 V) for one week. Sham threshold determination may be done during this visit, or during randomization visit (see below study week 2). RSC will schedule cardiovascular and sympathetic testing, if possible. The patient will also be instructed about neurobehavioral testing and will perform a practice administration of the DSST and PVT. Form 1 will be completed by RSC (remote #, current therapy status, non-dominant arm diameter, WatchPAT digit determination, medication reconciliation, sham threshold determination (volts), and active therapy setting (volts)). If needed, the patient will contact RSC after the appointment to provide the remote number. The patient will also be given an "on-study card" containing contact information for the research coordinator. The patient will be told to contact the coordinator if any health care providers intend to make changes to the patient's blood pressure medication. An enrollment questionnaire will be completed by the patient:
 - o Do you take any medications or substances to improve daytime alertness?
 - Do you take any medications or substances to improve sleep quality?
 - o How many hours do you sleep each night, on average?
 - ESS, ISI, FOSQ, Snoring VAS
- Washout Period 1 (Study Week 1): The patient will not use HGNS for 1 week
- Randomization Visit (Study Week 2 with [name] and RSC):
 - a. Patient will fill out "washout questionnaire":
 - Patient attestation statement about therapy non-use
 - Have you taken any substance to increase daytime alertness (e.g. caffeine)?
 - Have you taken any substance to improve sleep quality (e.g. alcohol)?
 - o Have you had any episodes of falling asleep while driving?

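### The drowsy-driving exclusion ends at implantation, so a sleep-related crash or near miss after implantation does not keep a patient out of about 42 days of washout and sham

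*Combined protocol and SAP*

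**What the plan says.** Section 2 (Exclusion Criteria) has one driving criterion. It covers falling asleep while driving that led to an accident or near miss, and its window is "within 1 year prior to HGNS implantation".

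Section 1 (Eligibility Criteria) requires all recruits to have the device already, with more than 20 hours of use per week at the therapeutic setting for more than one month. Section 4A describes what comes between surgery and that point:

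- The device stays off "for 1 month to allow for adequate healing".
- It is then activated and ramped up: "For the next month, the patient will have steadily increased stimulation strength by 0.1V every 2-3 nights".
- A titration sleep study follows at two months.

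The heading of section 4B puts enrolment at no fixed time: "Recruitment into the Cardiovascular Outcomes Study (variable months post-op".

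On Study Day 1 (section 4C), "HGNS therapy will be deactivated (set to 0.0 V) for one week". At the same visit, "An enrollment questionnaire will be completed by the patient". Its listed content is alertness aids, sleep aids, hours of sleep, ESS, ISI, FOSQ and a snoring scale. The question "Have you had any episodes of falling asleep while driving" appears only on the two washout questionnaires, at the randomization and crossover visits.

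Section 7 (Risk / Benefit) expects symptoms to go back to their pre-surgical state under sham. It advises avoiding driving, or taking more care, in that period.

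**The concern.** The hazard this criterion guards against arises when the study withdraws therapy, which first happens on Study Day 1. The look-back closes at implantation, possibly long before. A patient who crashed after falling asleep during the device-off month, during ramp-up or while on established therapy is eligible as the text stands. So is a patient implanted three years ago who had a near miss last month.

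Participant safety, and the safety of other road users, is at stake. The protocol already treats a sleep-related crash as a reason not to withdraw therapy; the criterion simply does not reach the most recent evidence. The protocol handles another hazard of stopping treatment differently: section 2 requires a pregnancy test, where applicable, before each washout. Driving risk has no comparable check before therapy is first stopped.

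**Working it through.** The documents give component durations but no total, so there is no stated figure to reproduce.

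**1. The unscreened interval (implantation to enrolment)**

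- Device off: 1 month (section 4A, implantation).
- Therapeutic use before enrolment: more than 1 month (section 1).
- Minimum: 1 + more than 1 = more than 2 months.
- If therapeutic use counts only from the titration study at 2 months (section 4A): 2 + more than 1 = more than about 3 months.
- Maximum: none stated (section 4B).

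The part most like the untreated state is the device-off month plus the ramp-up month: 1 + 1 = about 2 months. The rest is time on therapy.

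**2. Does anything else screen that interval?**

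| Provision | Section | Covers a post-implant crash or near miss before therapy is withdrawn? |
|---|---|---|
| Other eligibility criteria | 1, 2 | No; none concerns driving, and there is no investigator-discretion clause |
| Eligibility source documents | 4C, just before the timeline | None is designated to capture such an event |
| Enrolment questionnaire | 4C | No crash or near-miss question is listed; no cut-off or action is attached to the sleepiness scales |
| Washout questionnaires 1 and 2 | 4C | No; completed after the device has been at 0.0 V for a week, with no action stated for a yes |
| Driving advice | 7 | No; it is advice, worded for the sham period |

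**3. Time without effective therapy**

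- Washout 1: 7 days. Sham: 28 days. Washout 2: 7 days (sections 4C and 7).
- Total in either sequence: 7 + 28 + 7 = 42 days.
- Sham first: all 42 days are consecutive.
- Treatment first: 7 days, then 28 days on therapy, then 7 + 28 = 35 consecutive days.

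Sensitivity to other wording in the document:

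- With the 30-day sham in the section 3 hypotheses: 7 + 30 + 7 = 44 days.
- If the two-week washout in section 10 meant two weeks each time: 14 + 28 + 14 = 56 days.
- The note to Figure 3 says "We will leave +/- 14 days at each step to accommodate for scheduling issues, etc". If all three steps ran 14 days over: 21 + 42 + 21 = 84 days. This is an assumption, because the figure is not shown.

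**4. When the driving question is asked**

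- Sham first: after 7 of the 42 days, and again after all 42.
- Treatment first: after 7 and after 14 of the 42 days. The 28 sham days come last, and no driving question is listed after them. The content of the exit questionnaire is not given.

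**The case against.** The strongest defence is that the anchor was chosen for a reason. The risk of interest is driving with untreated sleep apnoea, and the pre-implant year samples that state directly. By the count above, only about two months of the gap resemble it; the rest is treated time and says less about untreated risk. This is a good argument for keeping the pre-implant year. It does not justify ignoring later events: the off and ramp-up months are both similar to the untreated state and more recent, and a crash despite therapy matters before that therapy is removed.

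The second defence is that the plan has other safeguards. The washout question is broader than crash or near miss, and it is asked before the next setting is programmed. Someone besides the coordinator attends the randomization visit. Weekly calls record adverse events in both periods, and the principal investigator judges relatedness (section 11). Patients are told before enrolment that symptoms may return. Because they are blinded, the driving advice can hardly be confined to the sham weeks in practice. These points count as mitigation. But the recording steps come after therapy has been withdrawn, the rest is information or advice, and no stated rule turns a positive answer into action.

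Three limits stand:

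- Section 7 says patients are likelier to be sleepy under sham; applying this to the washouts is inference.
- The 42 days apply to every participant, so they measure exposure and not how often the gap matters.
- The right length for the post-implant window is partly a matter of judgement.

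**Conclusion.** The concern holds. As written, the criteria admit a patient with a sleep-related crash or near miss after implantation to a nominal 42 days of washout and sham. The unscreened interval is more than 2 months, or more than about 3 months if counted from titration, and has no upper bound.

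This is a patient-safety improvement that should be made. It is not a flaw in the statistical design: no estimate, sample size, power figure or analysis is affected. The number of patients concerned is unknown, because the documents give no event frequency.

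The conclusion rests on a literal reading of the exclusion list and on the questionnaire content as listed. Consent pages were removed, so any driving warnings there cannot be judged.

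**What to change.** 1. Keep the pre-implant year and let the exclusion run from one year before implantation through enrolment. If excluding a long-implanted patient for one old near miss seems too strict, the sponsor could cap the post-implant look-back, provided it still covers the device-off and ramp-up months and the recent past.
2. At consent, before the device is set to 0.0 V, ask one question about any sleep-related crash or near miss since implantation.
3. State that the investigator reviews a positive washout answer before the next setting is programmed. This need not reveal the assignment.

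The cost is one eligibility phrase, one new enrolment question and one sentence on handling a positive answer. The downside is possibly a few ineligible patients; the documents do not allow a count. No statistical figure changes.

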 - 5. Exit Questionnaire
 - 6. The patient will resume usual care: the RSC will reprogram the patient's HGNS to the pre-study therapeutic amplitude and will reactivate the stimulation control range. The patient will be encouraged to contact the study team to address any problems or questions.

5. Variables:

Medical Chart: age, sex, race, smoking status, hypertension status, diabetes status, apnea-hypopnea index (AHI) from pre-operative sleep study, ODI from pre-operative study, pre-operative DISE report, history of PAP intolerance

Study Data (Clinical): body-mass index, current medications (recorded each study visit), therapy usage (hours/week)

Study Data (Experimental): mean systolic and diastolic blood pressures over 24 hours, mean systolic and diastolic blood pressures during sleep, WatchPAT ODI and AHI from both sham and active therapy tests, pre-ejection period (milliseconds), flow-mediated dilation, peripheral arterial stiffness (PWV in m/s, AIX, SEVR), Snoring Visual Analog Scale (VAS), Epworth Sleepiness Scale (ESS), Insomnia Severity Index (ISI), Functional Outcomes Sleep Questionnaire (FOSQ-10)

6. Analysis

The overall analysis plan is to examine changes in all cardiovascular endpoints over time (i.e., sham to treatment or treatment to sham) as well as internal correlation of these endpoints. Sex, a relevant biological variable, is a covariate in all analyses.

For **Aim 1**, we will perform a paired t-test to compare sham and active therapy 24-hour systolic ambulatory blood pressure values. Improvement in AHI will be calculated as the

difference between pre-operative and post-operative AHI. Multivariable linear regression models will be used to estimate associations between blood pressure reduction (outcome variable) and improvement in AHI (main effect variable) Final models will include age, sex, body-mass index, baseline systolic BP, baseline diastolic BP, antihypertensive medication use.

- H1: Therapeutic levels of HGNS will reduce mean 24-hour systolic pressures
- **H2:** Therapeutic levels of HGNS will further reduce mean sleep systolic and diastolic pressures

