Potential study risks: Patients will undergo laboratory testing of their cardiovascular system following each intervention arm. They will undergo pre-ejection period, by which an external chest monitor and electrocardiogram are used to calculate the time between electrical and mechanical motion of the heart. While muscle sympathetic nerve activity represents an invasive procedure, microneurography is a safe, well-tolerated, standard human research procedure that has been used in multiple studies with a range of patient diagnoses – greater than 200 procedures performed at Emory University by [name], collaborating investigator, without complication. Approximately 7% of subjects have discomfort, including tingling, soreness at the electrode insertion site, or muscle weakness in the leg 1 to 2 days following the procedure; this usually resolves within a week. There are no known long-term risks. Participants are free to discontinue microneurography at any time for any reason.

As part of the experimental study design, the subject will be assigned to a 4-week sham intervention period during which they will most likely experience a recurrence of symptoms of OSA that may have been alleviated by the HGNS during clinical care. As only patients who

had previously untreated OSA therapy are eligible for the study, these patients will experience a return to pre-operative symptoms. We have deliberately excluded patients who were actively using CPAP or other OSA therapy prior to HGNS surgery, as placing these subjects through a period of inadequate treatment (sham period) bears ethical concern. Subjects will be advised to avoid or exercise increased caution when driving or operating heavy machinery during the sham therapy period when they are more likely to feel sleepy. Additionally, patients will wear a blood flow measurement device for 24 hours, which is also well tolerated and does not disturb sleep or other daily activities. Wearing the WatchPAT device while sleeping may result in decreased sleep quality during the night of the testing. However, sleep quality typically returns to usual the following night, with no lasting effects noted.

Potential study benefits: This study is not designed to benefit subjects directly. However, the study results may help doctors to better understand sleep apnea and might be used to help people with sleep apnea in the future.

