Risk/Benefit Ratio: As there are few risks in measuring cardiovascular data apart from recurrence of OSA symptoms during the 4-week sham period and there are the possible benefits of better understanding sleep apnea and how to treat people with sleep apnea in the future, the risks of participating in this study are outweighed by the potential benefits.

8. Device Management

Penn owns WatchPAT and ambulatory blood pressure devices, which will be managed, dispensed, and received back from subjects by the study team. Recordings will be handled and scored in accordance with best clinical practices.

9. Feasibility

Sample Size Feasibility: We have recruited 17 subjects (16 have successfully completed the study) since January, 2018, and plan to complete recruitment in 2020.

Technical Feasibility: With regard to Aim 1, 16 subjects successfully completed both sets of 24-hour ambulatory blood pressure testing.

Project execution feasibility: PI has 50% protected research time through 2021. PI will devote 20% of his efforts to ensure the successful completion of this project.

10. Potential Pitfalls, Solutions, and Contingency Plans

1. Study Design

a) The study sample reflects a selective subset of patients with moderate-severe OSA, limiting the generalizability of these findings. Among others, the inclusion criteria are 1) unable to consistently use PAP, and 2) body-mass index < 32 kg/m². In clinical practice, this represents only 20% of the moderate-severe OSA population as BMI > 32 kg/m² is an exclusion criterion for HGNS and roughly 50% of patients can comply with PAP. From a population health perspective, however, this selected group represents a not insignificant 2% of the U.S. adult population. ⁴ Note: since this research protocol was created, BMI was

removed as an exclusion criteria for HGNS.

- b) We are performing measurements at 2 time points only, immediately after sham and treatment interventions. While we do not capture baseline values, these measures will allow us to compare the individual effects of sham and active therapy. We predict that a 2-week washout period, in contrast to the 1-week withdrawal period in the STAR trial, ²³ will provide a return to baseline for ABP at 2 weeks. ³¹

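### Section 7 claims an exclusion for OSA treatment used before surgery that the criteria in Sections 1 and 2 do not contain for non-PAP therapies

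*Combined protocol and SAP*

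**What the plan says.** Section 7 (Risk / Benefit, potential study risks) describes who is exposed to sham. It says that only patients who "had previously untreated OSA therapy are eligible for the study, these patients will experience a return to pre-operative symptoms". It continues: "We have deliberately excluded patients who were actively using CPAP or other OSA therapy prior to HGNS surgery". The reason given is that "placing these subjects through a period of inadequate treatment (sham period) bears ethical concern".

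Section 2 has one line on an OSA treatment other than HGNS: "Actively using positive airway pressure (PAP) therapy for treatment of OSA". Section 1 requires patients to be implanted already and to have used the device for more than 20 hours per week for more than 1 month. The present-tense line in Section 2 is therefore most naturally read as PAP use at enrolment.

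Three other places bear on the point:
- Section 10, Study Design item a: "Among others, the inclusion criteria are 1) unable to consistently use PAP", followed by a BMI limit.
- Section 5, the chart variables, which include "history of PAP intolerance".
- Section 4B, the eligibility source documents, which begin "Initial consult note, pre-implant sleep study, pre-implant DISE report".

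**The concern.** Section 7 uses the exclusion as an ethical safeguard: withdrawing a working treatment is presented as acceptable because nobody ends up worse off than before the operation. The safeguard protects patients only if the criteria applied at screening contain it. A screener works from Sections 1 and 2, and those sections say nothing about non-PAP therapy and nothing about treatment used before surgery.

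The exposure is not trivial. Under Section 4C each participant has two 7-day washouts at 0.0 V and 28 days of sham. That is 7 + 7 + 28 = 42 days without therapeutic stimulation, before the scheduling allowance of 14 days either way at each step. For a patient whose OSA was controlled by something else until implantation, sham could mean less treatment than before surgery, which Section 7 does not describe.

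**Working it through.** The plan states no figure on this point, so the check is a comparison of texts.

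**Step 1. List the criteria and see what each covers.**

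| Section | Criterion (paraphrased) | Names an OSA therapy other than HGNS? | Refers to OSA treatment before surgery? |
|---|---|---|---|
| 1 | Device implanted | No | No |
| 1 | Adequate device use before enrolment | No | No |
| 1 | English-speaking, able to consent | No | No |
| 2 | Remote model | No | No |
| 2 | Asleep-at-the-wheel event | No | No |
| 2 | Pregnancy | No | No |
| 2 | Active PAP use | Yes, PAP | No |
| 2 | Sham and therapeutic voltages too close | No | No |

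Total: 3 + 5 = 8 criteria. One names an OSA therapy other than HGNS. None covers non-PAP therapy, and none refers to OSA treatment before surgery.

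**Step 2. Compare the two rules.** Section 7 is wider than Section 2 in scope (CPAP and other therapies, against PAP only) and differs in timing (before surgery, against no stated time). The driving criterion in Section 2 is expressly tied to the year before implantation, so the plan does anchor a criterion to surgery where that is meant.

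**Step 3. Look for a rule elsewhere that closes the gap.**
- Section 10 covers inability to use PAP consistently. It is silent on other therapies.
- Section 5 collects PAP intolerance as a variable. It does not make it a condition of entry.
- Section 4B names documents against which criteria are verified. It adds no criterion.
- The questionnaire items listed in Section 4C ask about alertness and sleep substances, medication and symptoms. None names a non-PAP OSA treatment.

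**Step 4. Apply both rules to a test patient.** Take a patient who could not use PAP, was well controlled on a prescribed non-PAP therapy until implantation, and stopped it afterwards. The patient is hypothetical; the documents describe no such case.
- Nothing in this history fails any of the 8 criteria in Sections 1 and 2.
- The patient also satisfies the PAP condition in Section 10.
- Under Section 7 the patient is excluded.
- If enrolled, the patient had treated OSA before the operation and has neither the earlier therapy nor effective HGNS during sham. Describing sham as a return to the pre-operative state then understates the risk.

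**The case against.** **PAP is already dealt with.** A reader might infer that prior PAP users also slip through. The documents do not support that as a substantial gap. Section 10 gives PAP inability and the BMI limit together, calls the BMI limit an HGNS exclusion, and adds that it was later dropped for HGNS. The natural reading is that both are conditions for receiving the device, inherited because Section 1 admits only implanted patients. Section 2 also bars active PAP use. This objection stands, and it narrows the point to non-PAP therapy before surgery.

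**The harm is conditional.** It needs an earlier therapy that worked and was then stopped. Patients with moderate-severe OSA who accepted implantation under general anesthesia are less likely to have been well controlled. Section 7 also warns, correctly for everyone, that symptoms relieved by HGNS will probably recur. Driving cautions, weekly calls and questions about sleepiness at the wheel apply to all participants. This stands too: only the comparison with the pre-operative state may be inexact, and only for some patients.

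**Section 7 may simply be old text.** It still describes microneurography, which Section 3 says is not performed at this site. That may explain the mismatch but does not remove it. If Section 2 is the operative rule, Section 7 claims a protection that is not applied.

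**Conclusion.** The point holds in a limited form. A safeguard stated in Section 7 is not carried into the criteria for patients who used an effective non-PAP therapy up to surgery, and the sham risk may be understated for them. It is worth correcting because it concerns patient safety and costs little.

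Its size cannot be given. The planned sample is 60, and the documents do not say how many patients used a non-PAP therapy before implantation. The number is probably small. That is a judgement, resting on the population described.

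A reader might go further in two ways, and the documents support neither:
- **That ineligible patients were enrolled or harmed.** Section 9 says "We have recruited 17 subjects (16 have successfully completed the study) since January, 2018" but gives no treatment history, and no such patient is described.
- **That the primary comparison is biased or underpowered.** Sham and active values are compared within patients. The sample size inputs (difference 4 mmHg, standard deviation 11) do not depend on treatment before surgery. No bias or loss of power is claimed.

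The conclusion assumes that screening follows the labelled lists in Sections 1 and 2.

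**What to change.** Decide which rule is intended and make the sections agree.

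**If Section 7 is intended,** add an exclusion to Section 2 along these lines: patients who, up to the time of HGNS surgery, were actively using PAP or another prescribed OSA therapy (other than HGNS). The existing line on active PAP use can stay. Two parts of the wording matter. Without the exception for HGNS, a rule on any OSA therapy could be read to bar every participant, since Section 1 requires device use before entry. Restricting it to prescribed therapy avoids removing patients for trivial measures. Copying the PAP condition from Section 10 into Section 1 is not needed.

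**If the looser Section 2 rule is intended,** correct the Section 7 sentences on previously untreated patients and on the exclusion, and state the sham risk for patients treated by other means before surgery.

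**Cost.** The first option adds one criterion and one check in the initial consult note, already an eligibility source document. For patients implanted at Thomas Jefferson University, Section 12 says that only a patient list and contact details are sent, so the note may have to be requested or the patient asked at consent. Recruitment may slow slightly. The second option costs only a text correction.
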